8.2 Laboratory Evaluations

Pre Operative laboratory evaluations will include:

Complete Blood Count (CBC)

C-Reactive Protein (CRP)

Renal Function Test (RFT)

Hepatitis B and C

Electrocardiogram

Chest X-ray

Activated Partial Thrombin Time (aPTT)

Prothrombin Time (PT)

Hemoglobin A1c (HbA1c)

Post operative laboratory evaluations

Complete Blood Count (CBC)

C-Reactive Protein (CRP)

from which investigators will take data of C-reactive protein values in our study, to compare pre and post operatively.

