Total joint arthroplasty (TKA) is viewed as one of the most successful orthopedic surgeries for most end-stage joint diseases. In recent years, the concept of enhanced recovery after surgery (ERAS) has greatly improved the speed of rehabilitation after total joint arthroplasty. Patients feel more comfortable during the perioperative period and have shorter hospital stays with the administration of steroid administration. Dexamethasone plays an important role in ERAS due to its anti-inflammatory and pain reduction role. As, TXA can prevent the activation of plasminogen and delay fibrinolysis and reduce blood loss and the rate of blood transfusion perioperatively. Recent studies showed that dexamethasone may be administered multiple times peri operatively. A large number of studies confirmed that dexamethasone can reduce post operative pain and inflammation and shortens the length of hospital stay and combination pre operative tranexamic acid with dexamethasone reduces the limb swelling that improves the joint range of motion. There will be no risk of the interventional drug

Benefits will include that the drug is cost effective, easily available, reduce the post operative complications

3. Rationale

Previous studies showed the effects of peri-operative use of single dose of dexamethasone, and there is very little data available on effects of peri-op use of multiple doses of dexamethasone. There is no study that has been conducted yet, which compared the effects of peri-op use of 1 dose of dexamethasone and tranexamic acid with 2 doses of dexamethasone and tranexamic acid, on post operative range of motion and pain during rest and weight bearing on operated limb, length of stay in hospital and C-reactive protein.

4. Study Objectives

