4.1 Primary Objective

To evaluate the effectiveness of peri operative intravenous 2 doses of dexamethasone in lower limb joint/s replacement surgeries on postoperative C-reactive protein, post operative fatigue, postoperative joint range, post operative pain during rest and weight bearing, and length of hospital stay.

4.2 Hypothesis:

If hypothesis will get confirmed, then the peri operative use of 2 doses of dexamethasone with intravenous tranexamic acid, reduces the postoperative C-reactive protein, post operative fatigue, pain during rest and weight bearing, and length of hospital stay and improves the post operative joint range of motion.

If hypothesis will not get confirmed, then the peri operative use of 2 doses of dexamethasone with intravenous tranexamic acid, will not reduces the postoperative C-reactive protein, post operative fatigue, pain during rest and weight bearing, and length of hospital stay and and will not improve the post operative joint range of motion.

5. Material and Methods:

5.1 Study Design:

Randomized controlled trial with 2 arms

Arm 1: GROUP A will receive 1 dose of dexamethasone (10mg) with tranexamic acid (20mg/kg), peri operatively .

Arm 2: GROUP B will receive 2 doses of dexamethasone (2*10mg) with tranexamic acid (20mg/kg), peri operatively.

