10.3 Determination of Sample Size and Power Calculation

The calculated sample size, using total blood loss is 25 in each group and after adding 20% dropout the sample size will be $25+5=30$ in each group. The sample size is calculated using following information.

$Z_{1-\alpha/2}$ Level of significance=95%

μ_1 Expected mean change in total blood loss in Group A=93.80

μ_2 Expected mean change in total blood loss in Group B= 95.98

δ_1 Expected standard deviation in group A=3.88

δ_2 Expected standard deviation in group B=2.82

$Z_{1-\beta}$ power of the study= 80%

sample size in a group(n)= 38

After adding 20% drop out $38+8=46$ in each group.

Total sample size will be 92

No of groups/arms in study:

Type of comparison:

Superiority comparison

Type of configuration:

Parallel designs

Level of significance (Alpha level): 95 %

Power: 0.8 or 80 %

Allocation ratio: 1:1

Underlying population event rate:

Almost 90 percent of population undergoing total joint replacement, whether uni or bilateral would show the positive clinical outcomes with the use of 2 doses of dexamethasone.

Effect size of therapy: the clinical guidelines shows that each group of clinical trial must have at least 30 participants, so effect size is 92 more than sample size calculated, drop out patients percentages added.

Estimated loss to follow-up or refusals: Based on previous work in this population, 20 % will be lost to follow up or drop out from the trial.

10.4 Underlying population event rate:

The population enrolled in previous studies undergoing total joint replacement, whether unilateral or bilateral showed the positive clinical outcomes with the use of dexamethasone with tranexamic acid.

10.5 Estimated loss to follow-up or refusals: Based on previous work in this population, 20 % will be lost to follow up or drop out from the trial.

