11.3 Records to be kept

Total 4 questionnaires will be provided for each subject to record the data pre and post operative 1st day, 1st and 4th week after discharge. Subjects will be identified by the patient medical record number (MR no).

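### The only sentence on how CRP values will be compared gives a pre-versus-post contrast with no arm named, and should be reconciled with the protocol's two-arm superiority comparison

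*Protocol*

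**What the plan says.** CRP comes first among the outcomes in the primary objective (section 4.1): "To evaluate the effectiveness of peri operative intravenous 2 doses of dexamethasone in lower limb joint/s replacement surgeries on postoperative C-reactive protein". Section 8.2 lists CRP among both the pre-operative and the post-operative tests, and ends by describing them as the results "from which investigators will take data of C-reactive protein values in our study, to compare pre and post operatively". Section 11.3 provides four forms per patient to "record the data pre and post operative 1st day, 1st and 4th week after discharge".

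The between-arm question appears in other places. The rationale (section 3) says that no study has yet been done "which compared the effects of peri-op use of 1 dose of dexamethasone and tranexamic acid with 2 doses of dexamethasone and tranexamic acid", and CRP closes its list of outcomes. Section 5.1 describes a "Randomized controlled trial with 2 arms". Section 10.3 gives the type of comparison as "Superiority comparison" and the configuration as "Parallel designs", with 1:1 allocation.

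On method, section 10.2 says only that inferential and descriptive techniques will be used in SPSS. The protocol names no test, model or covariate for CRP, and nothing in it excludes adjustment for baseline.

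**The concern.** The protocol is not silent on the CRP contrast. It states one, and that contrast runs across time within patients and not across arms. A within-patient comparison shows whether CRP changed around surgery; it makes no use of the randomisation and cannot show whether a second dose changes CRP.

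If whoever writes the analysis follows section 8.2 to the letter, the likely product is a paired test in each arm. The natural misuse is then to read a significant change in one arm and a non-significant change in the other as a difference between doses. CRP is the first outcome named in the primary objective, so the sentence that defines its comparison should match the design.

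**Working it through.** **1. What contrast is the trial sized for?** Inputs from section 10.3 (for total blood loss): means 93.80 and 95.98, SDs 3.88 and 2.82, power 80%, and a significance level written as 95%, read here as two-sided alpha 0.05. For two independent means,

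n = (SD_A² + SD_B²)(z₀.₉₇₅ + z₀.₈₀)² / Δ²

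- Δ = 95.98 − 93.80 = 2.18, so Δ² = 4.7524
- SD_A² + SD_B² = 15.0544 + 7.9524 = 23.0068
- (1.960 + 0.842)² ≈ 7.849
- n = 23.0068 × 7.849 / 4.7524 ≈ 38.0 (37.997 unrounded), so 38 per group

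This reproduces the stated 38. The formula compares two independent groups, so the sizing is between arms and not paired. It uses blood loss, so it shows the intended type of contrast and nothing about CRP itself.

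**2. The statements side by side.**

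| Place | Contrast |
|---|---|
| Section 3 | one dose versus two doses, CRP among the outcomes |
| Section 5.1 | two randomised arms |
| Section 10.3 | parallel groups, superiority, 1:1 |
| Section 8.2 (CRP) | before versus after surgery, no arm named |

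The last row is the odd one out.

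**3. What the literal reading would do.** Suppose the true pre-to-post change is the same in both arms, so there is no dose effect, with 38 per arm and a separate two-sided 0.05 test in each. Let c be the true change in units of the SD of the change (assumed). By normal approximation, each arm is significant with probability p ≈ Φ(c√38 − 1.96), and exactly one arm is significant with probability 2p(1 − p).

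| c | p | exactly one arm significant |
|---|---|---|
| 0.3 | 0.456 | 0.50 |
| 0.5 | 0.869 | 0.23 |
| 0.8 | 0.999 | 0.003 |

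With a modest change, discordant results are common without any dose effect. With a large change, both arms are significant whatever the dose effect. Neither pattern answers the trial's question.

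**4. What baseline adjustment can gain over a between-arm change score.** Let r be the pre/post correlation and k the ratio of post-operative to pre-operative SD. The protocol gives neither, so both are assumed. The large-sample variance ratio is

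ANCOVA / change score = k²(1 − r²) / (k² + 1 − 2rk)

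| r | k = 1 | k = 2 |
|---|---|---|
| 0.2 | 0.96/1.60 = 0.60 | 3.84/4.20 = 0.91 |
| 0.3 | 0.91/1.40 = 0.65 | 3.64/3.80 = 0.96 |
| 0.5 | 0.75/1.00 = 0.75 | 3.00/3.00 = 1.00 |

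Against a comparison of post-operative values alone, the ratio is 1 − r² for any k: 0.96, 0.91 and 0.75. Apart from a degree of freedom, adjustment does not lose in these comparisons, but the size of the gain depends on two quantities that the protocol does not supply.

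**The case against.** The sentence closes a list of laboratory tests. It explains which results are extracted and why two time points are needed; it names no test and does not call for separate analyses by arm. Read with sections 3, 5.1 and 10.3, it fits a pre-to-post change compared between groups, which is a valid randomised comparison. This stands: a reader might infer that the protocol commits to within-arm testing, and it does not. What remains is that the only sentence on comparing CRP values leaves out the arms and allows the wrong reading.

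A reader might also infer that the lack of a baseline covariate is an error. It is not: covariates and model form are commonly left to the SAP, which is not shown, and no section rules adjustment out.

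Nor does section 10.3 show that CRP will be analysed as a change score. Its input, "Expected mean change in total blood loss in Group A=93.80", concerns blood loss and says nothing about CRP.

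Finally, a reader might expect adjustment to bring a large rise in power. That would need a CRP effect size and variances that the protocol does not give. Borrowing the blood-loss effect size and assuming equal SDs before and after surgery would produce one, but the advantage over a change score largely disappears when the post-operative SD is twice the pre-operative SD.

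**Conclusion.** The point holds as an inconsistency of wording. Section 8.2 frames the CRP comparison as pre versus post without naming an arm, and the rest of the protocol sets up a parallel superiority comparison of one dose with two. Taken alone, the section 8.2 contrast would not test that hypothesis.

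The discordance probabilities in step 3 apply only if separate within-arm tests were actually run, and they rest on assumed sizes of change. The benefit of baseline adjustment is real in direction but not quantifiable from the protocol: anywhere from a clear reduction in variance to practically none relative to a change score, depending on r and k. Adjustment is therefore recommended as the best form of the corrected sentence, and its absence is not counted as a separate fault.

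**What to change.** In section 8.2, replace the closing clause with wording such as: *to compare post-operative CRP between Group A and Group B, adjusting for pre-operative CRP (ANCOVA, on the log scale if skewed)*. The same form can be used for other outcomes for which a pre-operative value is recorded.

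The cost is a wording change only. Pre-operative CRP is already in the laboratory list and a pre-operative form already exists, so no extra data are needed. SPSS, the package named in section 10.2, fits the model, and the sample size is unaffected.

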8.3 Questionnaires

- Post operative identity consequences fatigue rating scale
- Numeric Pain rating Scale

9 CRITERIA FOR DISCONTINUATION

9.1 Permanent Treatment Discontinuation

- Drug-related toxicity
- Requirement for prohibited concomitant medications .
- Not completion of treatment as defined in the protocol.
- Request by subject to terminate treatment.
- Clinical reasons believed life threatening by the physician, even if not addressed in the toxicity section of the protocol.

9.2 Premature Study Discontinuation

- Failure by the subject to attend consecutive clinic visits at 1st week and 4th week after discharge.
- Request by the subject to withdraw.
- Request of the primary care provider if s/he thinks the study is no longer in the best interest of the subject.
- Subject judged by the investigator to be at significant risk of failing to comply with the provisions of the protocol as to cause harm to self or seriously interfere with the validity of the study results.
- A defined study endpoint reached.
- At the discretion of the IRB or investigator.

from which investigators will take data of C-reactive protein values in our study

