10 STATISTICAL CONSIDERATIONS

10.1 Blinding Procedures

The patients, trial participants, anesthesiologists, and data collectors will be blinded to allocation while assessors will know the allocation.

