11 DATA MANAGEMENT AND MONITORING

11.1 Key personal description

ROLE OF INVESTIGATOR: supervise and guidance of all study protocols

ROLE OF CO-INVESTIGATOR: allocation, screening and reassessments, at follow ups, of patients.

ROLE OF NURSING STAFF: taking data from patients under supervision of co-investigators.

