11.6 Follow-up of Discontinuations

The research team will complete all scheduled safety follow-ups with any patient who has prematurely terminated the trial because of a Serious Adverse Event, non-compliance with the protocol, or loss of eligibility, including definite contraindications

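### Section 9.2 lets randomised patients leave the study on grounds other than consent, and Section 11.6 then promises only safety follow-up, so week 1 and week 4 outcomes can be lost selectively

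*Protocol*

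**What the plan says.** Section 7.1 places all study drug between 10 minutes before surgery and closure of the incision. Stopping treatment has its own list in Section 9.1, so Section 9.2 concerns leaving the study.

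The grounds in Section 9.2 that matter here are:
- "Subject judged by the investigator to be at significant risk of failing to comply with the provisions of the protocol". The sentence goes on to require that the lapse would harm the patient or seriously damage the validity of the results.
- "A defined study endpoint reached", with no endpoint named.
- "At the discretion of the IRB or investigator", with no criterion attached.
- "Failure by the subject to attend consecutive clinic visits at 1st week and 4th week after discharge".

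Section 11.6 covers what follows: "The research team will complete all scheduled safety follow-ups with any patient who has prematurely terminated the trial". It names three reasons for termination: a serious adverse event, non-compliance, or loss of eligibility. Section 11.5 adds documented telephone calls for patients who do not return.

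On knowledge of the arm, Section 10.1 says "data collectors will be blinded to allocation while assessors will know the allocation". Section 11.1 gives co-investigators "allocation, screening and reassessments, at follow ups, of patients", and Section 11.4 has the assessor assign patients to groups. The blinded list in Section 10.1 does not include the investigators.

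**The concern.** Once the incision is closed, leaving the study changes only whether outcomes are recorded. Several Section 9.2 grounds depend on a judgement made after randomisation, when early pain and recovery can already be seen. Nothing reserves that judgement for someone blind to the arm. If removals relate to both arm and outcome, the two groups are no longer those that randomisation produced.

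A statistical analysis plan can define analysis sets and missing-data methods. It cannot recover pain, fatigue or range-of-motion values that the protocol allowed staff to stop collecting, so the point belongs in the protocol.

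**Working it through.** **Passages side by side**

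1. *Timing.* Treatment ends in theatre (7.1). The post-operative forms are for day 1 and for weeks 1 and 4 after discharge (11.3). A removal after day 1 leaves the day-1 form intact, and length of stay is known at discharge. The exposed data are the week 1 and week 4 assessments.
2. *Compliance.* Section 7.3 defines compliance as attending the week 1 and week 4 visits. Predicted non-compliance in 9.2 can therefore mean a patient expected to miss a visit, although the ground also needs the harm-or-validity condition.
3. *Follow-up after leaving.* Section 11.6 names safety follow-ups and three reasons. For a discretionary or endpoint removal, no follow-up is stated. The telephone calls in 11.5 are for patients who fail to return, not for patients the team removes.
4. *Knowledge of arm.* Assessors know it (10.1), the assessor assigns groups (11.4), and co-investigators allocate and reassess (11.1). The lead investigator's status is not stated.

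**Scale of the design (Section 10.3)**

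- Difference: 95.98 − 93.80 = 2.18. Pooled SD: √((3.88² + 2.82²)/2) = 3.392.
- n per arm = 2 × [3.392 × (1.960 + 0.842)/2.18]² = 38.0, which reproduces the protocol's 38. It becomes 46 per arm with the 20% addition.
- Design effect: 2.18/3.392 = 0.64 SD. It refers to total blood loss, which is not among the outcomes in Section 4.1, so it serves only as a yardstick.

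**Worst-case illustration**

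Assumptions: no true effect, normal outcomes, 46 per arm, and the k worst outcomes removed from one arm only. The mean shift is φ(z)/(1 − p), where p = k/46 and z is the upper-p normal quantile.

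- k = 2: p = 0.0435, z = 1.712, φ = 0.0922; shift = 0.0922/0.9565 = 0.096 SD, or 15% of 0.64.
- k = 5: p = 0.1087, z = 1.233, φ = 0.1864; shift = 0.1864/0.8913 = 0.209 SD, or 33% of 0.64.

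Two-sided type I error at nominal 0.05:

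| k removed | Simulated t-test, 46 vs 46 − k (40,000 runs) | Simulated shift (SD) |
|---|---|---|
| 0 | 0.05 | 0.00 |
| 2 | 0.08 | 0.09 |
| 5 | 0.18 | 0.20 |

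For k = 5, a simpler calculation treats 0.209 SD as a fixed shift with 38 per arm and gives about 0.15. It is lower because it uses fewer patients and ignores the reduced variance in the trimmed arm. Hence the range 0.15–0.18.

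**The case against.** The case on the other side has several parts, and much of it stands.

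- *The non-compliance ground is conditional.* It applies only where harm or a serious threat to validity is foreseen. This stands: it is one qualified ground and includes a patient-protection element worth keeping.
- *A reader might infer that discharge, which fixes length of stay, is the endpoint that ends participation.* The document as a whole does not support this. Week 1 and week 4 forms are scheduled for each subject (11.3, 14), and 9.2 itself refers to visits after discharge. The ground is undefined rather than an operating exit at discharge.
- *A reader might infer that outcome collection is barred after withdrawal.* Section 11.6 does not say so. The only scheduled post-discharge visits are weeks 1 and 4, which 7.3 describes as being for outcomes, so the promised follow-ups may well be those visits. But no section says that outcome forms are completed then, and 11.6 does not reach discretionary or endpoint removals.
- *A reader might infer that the removals are decided by someone who knows the arm.* Section 9.2 names the investigator, whose role in 11.1 is separate from the co-investigator's and whose blinding is not stated. What the text supports is that knowledge of the arm exists in the team and that nothing keeps it from these decisions. Data collectors are blinded.
- *The figures assume perfect one-arm selection.* This also stands. The protocol gives no rate of discretionary withdrawal.

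**Conclusion.** The point holds as a gap in the protocol: week 1 and week 4 outcomes **can** be lost selectively. The documents do not support saying that they **will** be.

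It rests on three textual facts. Exit grounds in 9.2 are not tied to consent, the commitment in 11.6 is limited to safety and to three reasons, and the blinding arrangements do not keep exit decisions away from knowledge of the arm.

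The upper end of the harm, under the stated worst case, is a shift of about 0.10 SD (2 of 46) or 0.21 SD (5 of 46), with type I error of about 0.08 or 0.15–0.18. These figures are not predictions. Removals balanced across arms, or unrelated to outcome, would do much less. The change is worth making because the loss could not be repaired later and the remedy is cheap.

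**What to change.** 1. **Section 11.6.** Replace the commitment to safety follow-ups with one to all scheduled safety and outcome follow-ups (week 1 and week 4 forms). Apply it to every randomised patient who discontinues for any reason, kept in the randomised arm, unless consent is withdrawn.
2. **Section 9.2.** Delete the ground of reaching a defined study endpoint. State that the investigator's non-compliance and discretion grounds do not by themselves end outcome collection. Leave the IRB's authority and the patient-harm provision as they are; deleting every discretionary ground would remove both.

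The cost is a few lines of wording, plus existing outcome forms for a few more patients at visits already scheduled.

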10 STATISTICAL CONSIDERATIONS

10.1 Blinding Procedures

The patients, trial participants, anesthesiologists, and data collectors will be blinded to allocation while assessors will know the allocation.

10.2 Sample Size and Accrual

IBM SPSS Statistics 21 software will be used to analyze the data.

Methods of analyzing the data will include inferential and descriptive statistics

10.3 Determination of Sample Size and Power Calculation

The calculated sample size, using total blood loss is 25 in each group and after adding 20% dropout the sample size will be $25+5=30$ in each group. The sample size is calculated using following information.

$Z_{1-\alpha/2}$ Level of significance=95%

μ_1 Expected mean change in total blood loss in Group A=93.80

μ_2 Expected mean change in total blood loss in Group B= 95.98

δ_1 Expected standard deviation in group A=3.88

δ_2 Expected standard deviation in group B=2.82

$Z_{1-\beta}$ power of the study= 80%

sample size in a group(n)= 38

After adding 20% drop out $38+8=46$ in each group.

Total sample size will be 92

No of groups/arms in study:

Type of comparison:

Superiority comparison

Type of configuration:

Parallel designs

Level of significance (Alpha level): 95 %

Power: 0.8 or 80 %

Allocation ratio: 1:1

Underlying population event rate:

Almost 90 percent of population undergoing total joint replacement, whether uni or bilateral would show the positive clinical outcomes with the use of 2 doses of dexamethasone.

Effect size of therapy: the clinical guidelines shows that each group of clinical trial must have at least 30 participants, so effect size is 92 more than sample size calculated, drop out patients percentages added.

Estimated loss to follow-up or refusals: Based on previous work in this population, 20 % will be lost to follow up or drop out from the trial.

10.4 Underlying population event rate:

The population enrolled in previous studies undergoing total joint replacement, whether unilateral or bilateral showed the positive clinical outcomes with the use of dexamethasone with tranexamic acid.

10.5 Estimated loss to follow-up or refusals: Based on previous work in this population, 20 % will be lost to follow up or drop out from the trial.

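### Section 10.3 gives two incompatible sample sizes for one set of inputs (25 and 38 per group), writes alpha as 95%, and enters a head count as the effect size

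*Protocol*

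**What the plan says.** All the statements at issue are in Protocol section 10.3.

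- **First sample size.** The section begins "The calculated sample size, using total blood loss is 25 in each group". It adds 5 for dropout to reach 30, and says that the information that follows was used.
- **Inputs.** "Expected mean change in total blood loss in Group A=93.80" and "Expected mean change in total blood loss in Group B= 95.98", with SDs of 3.88 and 2.82, 80% power and 1:1 allocation. No unit is given.
- **Second sample size.** The same list closes with "sample size in a group(n)= 38". Adding 8 for dropout gives 46 per group, and then "Total sample size will be 92".
- **Significance level.** It appears as "Level of significance=95"% beside the symbol for the two-sided normal quantile, and again as "Level of significance (Alpha level): 95" %.
- **Effect size.** The line for the effect of therapy says that "each group of clinical trial must have at least 30 participants, so effect size is 92 more than sample size calculated", and ends by noting that dropout has been added.

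Two other places bear on the point. Section 5.3 plans 8 patients a month for 12 months. Section 4.1 lists C-reactive protein, fatigue, joint range, pain at rest and on weight bearing, and length of stay. It does not list blood loss.

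**The concern.** A sample-size section should let a reader take the stated inputs, apply the stated error rates and arrive at one number. Here the same outcome and the same inputs are said to give both 25 and 38 per group. A reader who starts at the top of the section meets the number that the inputs do not support.

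The type I error rate is the second problem. It is one of the few design quantities that must be stated without ambiguity, and here a confidence level stands under the name of alpha. Third, the line where the assumed treatment effect should be stated holds a participant count, so the difference that the trial is powered for has to be worked out from the means.

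What is at stake is whether the calculation can be reproduced and whether the error rate is stated correctly. The planned enrolment is not at stake.

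**Working it through.** **Inputs (Protocol 10.3).** Means 93.80 and 95.98; SDs 3.88 and 2.82; power 80%; allocation 1:1; dropout 20%. Assumption: the 95% is a confidence level, so alpha = 0.05. The quantile notation used in the section implies a two-sided test.

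**Step 1: the assumed effect.**
- Difference: 95.98 − 93.80 = 2.18.
- Sum of variances: 3.88² + 2.82² = 15.054 + 7.952 = 23.007.
- Standardised difference: 2.18 / √(23.007/2) = 2.18 / 3.392 = 0.643.

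**Step 2: reproduce the plan's n (normal formula).**
n per group = (z₀.₉₇₅ + z₀.₈₀)² × (SD_A² + SD_B²) / difference²
= (1.960 + 0.8416)² × 23.007 / 2.18²
= 7.849 × 23.007 / 4.752 = 37.997, i.e. 38.

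The stated 38 reproduces. The t-based calculation gives 38.98, i.e. 39.

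**Step 3: try to reproduce 25.**

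| Variant | n per group |
|---|---|
| One-sided 0.05, 80% power | 30 |
| Two-sided 0.10, 80% power | 30 |
| One-sided 0.10, 80% power | 22 |
| Two-sided 0.20, 80% power | 22 |
| SD 3.88 in both groups, two-sided 0.05 | 50 |
| SD 2.82 in both groups, two-sided 0.05 | 27 |
| Average SD (3.35), two-sided 0.05 | 38 |

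No variant tried gives 25. The nearest (27) drops the group A SD, so it is not the listed input set.

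**Step 4: power at the various group sizes (two-sided 0.05).**
Power = Φ(2.18 / √(23.007/n) − 1.960). For n = 25: 2.18 / 0.9593 = 2.272, and Φ(0.313) = 0.623.

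| n per group | Normal formula | t-test |
|---|---|---|
| 25 | 62.3% | 60.5% |
| 30 | 70.2% | 68.7% |
| 36.8 | 78.7% | 77.6% |
| 38 | 80.0% | 79.0% |
| 46 | 86.9% | 86.2% |

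**Step 5: dropout and totals.**
- The plan multiplies by 1.2: 25 × 1.2 = 30, and 38 × 1.2 = 45.6, i.e. 46. Totals are 2 × 30 = 60 and 2 × 46 = 92.
- If 20% of 46 are lost, 46 × 0.8 = 36.8 remain, which is just under 38.
- Dividing by (1 − 0.2) gives 38 / 0.8 = 47.5, i.e. 48 per group and 96 in total.
- Planned accrual in section 5.3: 8 × 12 = 96.

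**The case against.** The best defence is that nobody would be misled about the size of the trial. The figures 38, 46 and 92 form a chain that reproduces from the inputs, and 92 recurs in the effect-size line. Accrual of 96 over the year fits 92 and not 60. The 25/30 sentence looks like leftover text, although that is an inference. The 95% beside a two-sided quantile is plainly a confidence level, and reading it so changes no number. The assumed effect is also present, since the means and SDs are listed. The effect-size line, read to its end, can be taken as the calculated number plus dropout.

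Most of this stands, and it rules out several stronger readings:

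- *The trial has only 62% power.* That figure describes 25 per group, and the stated total of 92 rules that design out.
- *The trial would be tested at alpha 0.95.* The n of 38 arises only with 0.05, so the label is wrong and the calculation is not.
- *No effect was assumed.* It was; it is simply not stated on its own line.
- *The dropout allowance leaves the trial short.* Sections 7.3 and 9.2 tie non-compliance and discontinuation to visits after discharge. When blood loss is measured is not stated, so patients lost later may still have it.

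The defence does not remove the errors. The 25/30 sentence is current text with nothing to mark it as superseded. The alpha label is wrong in two separate places. Neither looks like damage from text extraction, because both dropout sums are printed whole. Nor is this detail that a protocol leaves to the SAP: the protocol gives the figures, and they conflict.

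**Conclusion.** The point holds as a correction of stated figures. Section 10.3 ties 25 and 38 per group to one outcome and one input list, and only 38 follows (37.997 by the normal formula, with 95% read as two-sided alpha 0.05). The gap between the two is 62.3% against 80.0% power on the plan's own inputs. The alpha label is wrong twice but does not affect n. The effect-size line gives a head count where the effect should stand.

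The operative total of 92 is recoverable and is not called into question by these errors. A reader might infer from this that 92 is adequate for the trial's objectives. The document does not support that either: every power figure here concerns total blood loss, which is not among the section 4.1 outcomes, and says nothing about power for those outcomes.

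Minor and conditional: if the 20% lost also lack the sizing outcome, 36.8 per group remain and power is 78.7% (normal) or 77.6% (t-test). If none of them lack it, 46 per group gives 86.9% (normal). At worst the shortfall by the plan's own formula is 1.3 points.

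**What to change.** Changes within Protocol section 10.3:

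1. Remove the 25/30 sentence, or have the sponsor say where it came from and reconcile it with 38/46/92.
2. Write two-sided alpha = 0.05 in both places that now give 95%.
3. Replace the effect-size line with the assumed difference in total blood loss: 2.18, SDs 3.88 and 2.82, standardised about 0.64, with the unit of measurement.
4. State that 80% power refers to 38 evaluable patients per group by the normal formula (about 79% by t-test), and to total blood loss only, which is not a section 4.1 outcome.
5. State whether patients lost to follow-up are expected to lack the blood-loss measurement. If so, give power after 20% loss from 46 per group as about 78–79%.

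The cost is a wording and number correction in one section, with no added patients, visits or time. These edits make the existing calculation readable; they do not justify 92 for any other outcome.
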